10.3.5. Secondary Endpoint Analyses

The analysis of technical success which is reported by the investigator will be conducted on the mITT analysis set. The endpoint will be considered successful if the lower bound of the 2-sided 95% normal approximation based confidence interval for the rate is greater than a performance goal of 79%.

The analyses of the remaining secondary effectiveness endpoints listed below will be conducted on the PP analysis set using the observed data.

- The ability to retain embolic coils within aneurysm immediately post-procedure as reported by the independent core laboratory
- Complete aneurysm occlusion at 3 years and 5 years as reported by the independent core laboratory
- Adequate aneurysm occlusion at 1 year, at 3 years and 5 years as reported by the independent core laboratory
- The percentage of target aneurysms that are retreated through the 1 year, 3 year and 5 year as reported by the investigator
- The percentage of subjects with significant stenosis defined as > 50% at implant site at 1 year, 3 years and 5 years as reported by the independent core laboratory
- The percentage of subjects with mRS 0-2 at 1 year, 3 years and 5 years

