4.4.2. Handling of Participant Withdrawals or Termination

Subjects that withdraw consent after treatment are not required to undergo follow-up after withdrawal. They will not be replaced and will be considered part of the subject cohort. The reason for early withdrawal will be documented in the source documents and case report forms.

In the event a subject withdraws from the study, their data will be excluded from the data analysis from the time of withdrawal going forward. All data collected prior to withdrawal will be included in the data analysis.

5. Study Device

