10.3. Analyses to be Conducted

10.3.1. General Conventions

Standard descriptive summaries for continuous data include the number of observations with data, number of observations with missing data, mean, standard deviation, median, minimum, and maximum values. For categorical data, the count and percent will be provided. Percentages will be based on the number of subjects without missing data.

Analyses will take place using SAS statistical software version 9.4 or later in a server environment.

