10.3.4. Primary Endpoint Analyses

Primary Safety Endpoint

The primary safety endpoint analysis will be conducted on the mITT analysis set.

If a subject experienced a death due to neurological causes or a major ipsilateral stroke in downstream territory within a year post-procedure then subject will be deemed a failure on the endpoint. If a subject completed the 1 year follow up and did not experience any such event then subject will be deemed a success on the endpoint. If a subject did not complete the 1 year follow up and did not experience such event then the subject will be imputed with a multiple imputation method that will make use of the similarities between the subject's demographic, procedural, and aneurysm characteristics with those of the subjects with a non-missing endpoint (those who either experienced an event and those who completed the study without experiencing an event). The imputation method will also account for the length of time between the procedure and the last time the subject was seen. The longer that time period is, the less likely the subject will be imputed with an event.

Subjects for whom implantation of the PulseRider was attempted but not successful will be followed up to a year. Any safety events which occur due to attempted implant or from retreatment, and which meet the primary safety endpoint definition will count as failures in the analysis. If such a subject is lost to follow-up then subject will be imputed with data based on other subjects for whom the implantation was not successful but who were not lost to follow-up.

The multiple imputation method results in a large collection of imputed datasets. The proportion of primary endpoint events and its variance is computed for each dataset. Within and between imputation variances are then combined according to Rubin's method [Rubin 1996] in order to produce a single variance estimate for the proportion of events.

The endpoint will be considered successful if the upper bound of the 2-sided 95% normal approximation based confidence interval for the rate of events is less than a performance goal of 15%.

Primary Effectiveness Endpoint

The primary effectiveness endpoint analysis will be conducted on the PP analysis set.

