10.3.6. Additional Endpoint Analyses

The analyses of the percentage of target aneurysm ruptures up to 1 year, 3 years and 5 years post-procedure and of the percentage of no migration (defined as ≤ 2 mm) of the device at 1 year, 3 years and 5 years post-procedure will be conducted on the PP population using the observed data. Both endpoints are evaluated by the independent core laboratory.

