10.3.9. Handling of Missing Data

Missing primary safety and effectiveness endpoint data will be imputed as per the multiple imputation method described in section 10.3.4. The secondary effectiveness endpoint is expected to have minimal to no missing data and analysis will not make use of any imputations.

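### Cumulative retreatment and rupture to 3 and 5 years are crude percentages with no stated rule for subjects who leave event-free, so the result depends on the denominator chosen

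*Combined protocol and SAP*

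**What the plan says.** Section 10.3.5 includes among the secondary endpoints "The percentage of target aneurysms that are retreated through the 1 year, 3 year and 5 year as reported by the investigator", and gives the method for the group: "The analyses of the remaining secondary effectiveness endpoints listed below will be conducted on the PP analysis set using the observed data". Section 10.3.6 covers "The analyses of the percentage of target aneurysm ruptures up to 1 year, 3 years and 5 years post-procedure" and says that this analysis, with device migration, "will be conducted on the PP population using the observed data".

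Three other statements bear on the denominator:
- Section 10.3.1: "Percentages will be based on the number of subjects without missing data".
- Section 4.4.2, on subjects who withdraw: "All data collected prior to withdrawal will be included in the data analysis".
- Section 10.3.9: "The secondary effectiveness endpoint is expected to have minimal to no missing data and analysis will not make use of any imputations". The singular most naturally refers to technical success, the only secondary endpoint with a hypothesis test.

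No Kaplan-Meier, cumulative-incidence or other method that adjusts for censoring appears in the document. By contrast, the primary safety analysis in Section 10.3.4 does use follow-up time for early leavers: "The imputation method will also account for the length of time between the procedure and the last time the subject was seen".

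**The concern.** A percentage retreated through 5 years is a cumulative risk, and some subjects will not be followed that long. Section 10.3.1 removes subjects with missing data from the denominator but does not define missing for a cumulative event. Consider a subject who is event-free at 2 years and then leaves:

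- If the subject is treated as missing, the subject drops out of the denominator. A subject retreated before leaving stays in, because Section 4.4.2 keeps data from before withdrawal. The rate is then too high.
- If every PP subject stays in the denominator, the unobserved years count as event-free. The rate is then too low.
- If only subjects followed to the time point are used, the rate is unbiased under independent dropout, but retreatments seen before dropout are discarded, contrary to Section 4.4.2.

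Section 7.13 adds to the doubt, since a subject is not classed as lost before the last study visit. Two analysts could follow the text and report different 3- and 5-year rates from the same data. What is at stake is how the long-term retreatment and rupture rates read in an application for approval, not whether the study succeeds.

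**Working it through.** **Plan's own figure.** The plan states no expected rate, precision or dropout for these endpoints, so there is nothing to reproduce. Section 10.2 gives 10% attrition, in support of power for the 1-year primary endpoints (160 × 0.9 = 144). No 3- or 5-year figure is given.

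**Assumed inputs (not from the documents).** Five-year retreatment risk F = 12% in the absence of death, with 60% of events spread evenly over the first 18 months and 40% over the remaining 3.5 years. Deaths M = 5%. Dropout D = 10%, 25% or 35%. Death and dropout are spread evenly over 5 years. Event, death and dropout are independent.

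**Step 1: event timing.** Mean event time = 0.6 × 0.75 + 0.4 × 3.25 = 1.75 years, or 0.35 of 5 years. Mean squared time = 0.6 × 0.75 + 0.4 × 11.583 = 5.083, or 5.083 / 25 = 0.2033 on the same scale.

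**Step 2: target.** Cumulative incidence with death competing = F × (1 − M × 0.35) = 0.12 × 0.9825 = 11.8%.

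**Step 3: observed events as a share of all PP subjects.** A = F × [1 − (D + M) × 0.35 + D × M × 0.2033].
- D = 10%: 0.12 × 0.9485 = 11.4%
- D = 25%: 0.12 × 0.8975 = 10.8%
- D = 35%: 0.12 × 0.8636 = 10.4%

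**Step 4: events / (events + event-free completers).** Event-free completers C = (1 − F)(1 − D)(1 − M).
- D = 10%: C = 0.7524; 0.1138 / 0.8662 = 13.1%
- D = 25%: C = 0.6270; 0.1077 / 0.7347 = 14.7%
- D = 35%: C = 0.5434; 0.1036 / 0.6470 = 16.0%

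**Step 5: event-free deaths counted as known.** Such a subject's status is known. Deaths seen before dropout and before any event are M times the average, over the 5 years, of (1 − D × s/5) × (1 − risk to s). By numerical integration this is 0.0438 at D = 10% and 0.0404 at D = 25%. Adding them to the Step 4 denominators gives 0.1138 / 0.9101 = 12.5% and 0.1077 / 0.7751 = 13.9%.

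| Dropout by 5 years | All PP | Events + completers | Same, deaths known | Target |
|---|---|---|---|---|
| 10% | 11.4% | 13.1% | 12.5% | 11.8% |
| 25% | 10.8% | 14.7% | 13.9% | 11.8% |
| 35% | 10.4% | 16.0% | not needed | 11.8% |

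**Cross-check under a different model.** Constant hazards, true risk 10%, dropout 30%, no deaths. Hazards over 5 years: −ln 0.9 = 0.1054 and −ln 0.7 = 0.3567. All PP: 0.1054 / 0.4621 × (1 − 0.9 × 0.7) = 8.4%. Events + completers: 0.0844 / (0.0844 + 0.63) = 11.8%. Completers only: 10.0%. In simulation Kaplan-Meier gave 10.1%. The directions agree.

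Rupture was not quantified. A completers-only rate could be biased downward there even if other dropout is independent, because a rupture can itself cause death or exit.

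**The case against.** The strongest reply has five parts.

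1. **The denominator is inferred.** Section 10.3.1 is a general convention, and Section 4.4.2 sets no denominator. A reader might infer that the plan prescribes events over events plus completers, so that the reported rate must be too high. The documents do not support that. It is the most natural reading, but it is not stated for these endpoints.
2. **Not every crude percentage is biased.** A completers-only rate is unbiased under independent dropout. This stands, although that rate discards recorded events.
3. **The size is assumed.** At 10%, the only attrition figure in the plan, the errors are about −0.4 points (11.4 against 11.8) and +0.7 to +1.3 points (12.5 and 13.1 against 11.8). Sampling error is larger: 18 events in an assumed 150 subjects has an exact 95% interval of about 7.3% to 18.3%. This stands. However, that 10% supports a 1-year analysis, and 5-year dropout may be higher.
4. **The endpoints carry little formal weight.** A reader might take retreatment as the main durability result. The plan lists it unranked, beside complete and adequate occlusion at 3 and 5 years, and rupture is only an additional endpoint. Neither has a hypothesis, a performance goal or a part in study success. This stands.
5. **A separate SAP may settle it.** Section 10 defers derivation detail to a separate document. That document is not in the text available, so its content cannot be judged either way.

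**Conclusion.** The point holds in limited form. Two cumulative endpoints are to be reported as crude observed percentages, and the text leaves open how event-free leavers count. The two denominators that keep all recorded events err in opposite directions. Under the assumed 12% risk and 5% deaths, the gap between them is 1.7 points at 10% dropout (13.1 − 11.4), 3.9 at 25% (14.7 − 10.8) and 5.6 at 35% (16.0 − 10.4). These figures rest on independent dropout and on event, death and dropout rates that the documents do not supply. They apply to retreatment only. No decision rule, sample size or primary result changes, so this is a minor point. It is worth making because a better estimator is available at little cost.

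**What to change.** In Sections 10.3.5 and 10.3.6, estimate retreatment and rupture at 1, 3 and 5 years by cumulative incidence from the index procedure date, using the Aalen-Johansen estimator with death as a competing event and censoring at last contact. Give 95% confidence intervals and numbers at risk, and show the raw counts beside them. For rupture, state that a death caused by rupture counts as the event, not as a competing event. Name this one estimand: Kaplan-Meier with deaths censored targets a different quantity (12% against 11.8% in the example above).

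The cost is a change of wording and one standard procedure. Retreatment is already captured in the eCRF (Section 7.11), neurological events are reportable (Section 8.1.1), and the scheduled visits and calls (Section 7.7) supply last-contact dates. No new visits or subjects are needed. The downside is a slightly less simple table.

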- **National Institutes of Health Stroke Scale – NIHSS.** The NIHSS is a standardized clinical assessment tool that provides a quantitative measure of stroke-related neurologic deficit. It is widely used to evaluate stroke severity, determine appropriate treatment, and predict patient outcome. The NIHSS will be performed by qualified personnel. All study personnel performing the NIHSS assessment will be required to have training on the administration of the NIHSS assessment. A valid certification of completion of training will be stored in the site study files.
- **Modified Rankin Scale – mRS.** The mRS is a scale commonly used to measure the degree of disability or dependence in the daily activities in patients following stroke or other neurologic event and is conducted by qualified personnel. It is a scale with six categories ranging from no symptoms to severe disability and death. All study personnel

performing the mRS assessment will be required to have training on the administration of the mRS assessment. Documentation of completion of training will be stored in the site study files and updated at least every 2 years.

- **Baseline aneurysm imaging evaluation.** The baseline imaging evaluation may be a DSA or CTA. The baseline imaging must be reviewed and approved by the Image Screening Committee. As the status of the target aneurysm may change between the baseline image and procedure, a DSA is required prior to enrollment on the procedure day to confirm that the subject remains eligible for the study.
- **Image Screening Committee.** During initial subject screening, the site will submit a de-identified image (either DSA or CTA) to the core lab. Core lab personnel will submit the de-identified baseline image to the Image Screening Committee who will review the image for approval or disapproval. The decision of the committee will be based on their review of the appropriateness as outlined in the Image Screening Committee charter. Upon decision from the Image Screening Committee, the site will be informed of the subject approval/disapproval.

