10.1.6. Analysis Datasets

Modified Intent to Treat Analysis Set

The mITT analysis set consists of all enrolled subjects in whom treatment with the PulseRider device is attempted as defined by advancement of any portion of the PulseRider device outside of the distal end of the microcatheter inside the subject. This includes subjects in which the PulseRider is not fully advanced outside of the microcatheter. It is possible that the PulseRider device may not reach the target aneurysm, and as a result the treating physician does not advance the device outside of the distal end of the microcatheter. In the rare event that this happens, the subject will not be considered part of the mITT population and will instead be followed for 30 days.

Per Protocol (PP) Analysis Set

The PP analysis set consists of all subjects who meet the following criteria:

- there are no major deviations from the protocol eligibility criteria or DAPT requirements
- the subject is successfully implanted with the PulseRider device

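### mRS 0-2 is reported on per-protocol observed data: failed implants are excluded by rule and deaths have no stated rule, so the good-outcome rate may be overstated

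*Combined protocol and SAP*

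**What the plan says.** All references are to the combined protocol and SAP.

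- **Analysis set and data.** For every secondary effectiveness endpoint other than technical success, section 10.3.5 states: "The analyses of the remaining secondary effectiveness endpoints listed below will be conducted on the PP analysis set using the observed data". The last item in that list is "The percentage of subjects with mRS 0-2 at 1 year, 3 years and 5 years".
- **PP membership.** Section 10.1.6 requires that "the subject is successfully implanted with the PulseRider device" and that "there are no major deviations from the protocol eligibility criteria or DAPT requirements". Death is not a reason for exclusion.
- **Denominator.** Section 10.3.1: "Percentages will be based on the number of subjects without missing data".
- **Missing data.** Section 10.3.9: "The secondary effectiveness endpoint is expected to have minimal to no missing data and analysis will not make use of any imputations". The singular wording may be meant only for technical success, but section 10.3.5 separately fixes observed data for mRS.
- **The scale.** Section 7.2.1 says of the mRS: "It is a scale with six categories ranging from no symptoms to severe disability and death". No section says how a death before the visit enters the mRS 0-2 rate.
- **Failed implants.** Section 10.3.4 follows subjects with an attempted but unsuccessful implant for up to a year. It counts their qualifying events as failures on the primary safety endpoint, which uses the mITT set. For subjects without an implant, the footnote to Table 7.15A waives the 1-year DSA and nothing else.

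**The concern.** Exclusion criterion 4 keeps out anyone with a baseline mRS of 3 or more, so the trial population starts at mRS 0-2 and this endpoint in effect measures loss of function. Two groups who may have lost function are at risk of not being counted.

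The first is subjects in whom the device left the microcatheter but was not successfully implanted. An attempt can itself cause disability, and the plan accepts this for the primary safety endpoint. Yet these subjects, with the major eligibility and DAPT deviators, are outside the PP set and so outside the mRS rate.

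The second is subjects who die before the visit. Scheduled mRS assessments take place at visits and telephone calls (section 7.7, Table 7.15A), and section 7.6 adds one after a stroke or suspected stroke. A subject who died earlier has no assessment at 1, 3 or 5 years. Under the observed-data convention, one analyst could treat that subject as missing and another could count the death as a poor outcome. Both could claim to follow the plan, and they would report different rates.

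Other analyses do not fill the gap. The primary safety endpoint covers neurological death and major ipsilateral stroke and stops at 1 year. The adverse event tables report deaths but not functional status. The missing-data sensitivity analyses in section 10.3.10 cover only the primary endpoints.

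**Working it through.** The plan gives no expected rate, performance goal or power for mRS 0-2, so there is no figure for this endpoint to reproduce. The one stated figure tied to implant failure is in section 10.1.2: with 160 subjects, technical success of at least 85% is needed to beat 79%.

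**Check of that figure.** The normal-approximation lower bound is p − 1.96·√(p(1 − p)/n).
- 136/160 = 85.0%: 0.850 − 1.96·√(0.85 × 0.15/160) = 0.795, which passes.
- 135/160 = 84.4%: 0.844 − 1.96·√(0.844 × 0.156/160) = 0.787, which fails.

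The 85% reproduces. It means that up to 24 of 160 implants could fail with the technical-success test still met. This is an outer bound for illustration, not a forecast: section 1.3.2 reports 34 of 34 successful placements in the earlier HDE study.

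**Part 1: deaths.** Let g be the proportion of survivors with mRS 0-2 and m the proportion who have died. The rate is g if deaths are dropped and g(1 − m) if death counts as not mRS 0-2. The difference is g·m. Assume g = 0.88 and m from 2% to 10%; neither figure is in the documents.

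| Deaths | Deaths dropped | Death counted as not 0-2 | Difference (points) |
|---|---|---|---|
| 2% | 88.0% | 0.88 × 0.98 = 86.2% | 1.8 |
| 5% | 88.0% | 0.88 × 0.95 = 83.6% | 4.4 |
| 10% | 88.0% | 0.88 × 0.90 = 79.2% | 8.8 |

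If deaths are scored on the scale, this difference is zero.

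**Part 2: failed implants.** Let f of 160 attempts fail, q be the mRS 0-2 rate among those subjects, and p be the PP rate with deaths counted. The mITT rate is [(160 − f)·p + f·q]/160, so PP minus mITT equals (f/160)(p − q). The sign depends on whether failed-implant subjects do worse or better than implanted subjects with deaths counted.

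A second set of assumptions, also not in the documents, shows both parts together:
- 95% of implanted survivors have mRS 0-2;
- f runs from 0 to 24, and q from 70% to 95%;
- 0 to 11 implanted subjects die. The 11 is 7% of 160. It borrows the anticipated rate of the primary safety composite, which also includes strokes and ends at 1 year.

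Major eligibility and DAPT deviators are ignored.

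Example with 24 failed implants and 5 deaths:
- PP, deaths dropped: 95.0%.
- PP, deaths counted: 0.95 × 131/136 = 91.5%, so dropping deaths adds 3.5 points.
- mITT, deaths counted: (0.95 × 131 + 24q)/160 = 88.3% at q = 70% and 92.0% at q = 95%.

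Over the whole range:
- Dropping deaths adds 0 to 7.7 points (maximum 0.95 × 11/136).
- Leaving out failed implants changes the rate by between −1.2 points (24/160 × (0.873 − 0.95), 11 deaths) and about +3.7 points (24/160 × (0.95 − 0.70), no deaths).
- The two together give 0 to 10.3 points.

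With no failed implants and 3 deaths, the figures are 95.0% against 0.95 × 157/160 = 93.2%.

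**The case against.** A reader might infer that the plan removes deaths from the denominator and that the rate is therefore overstated. The documents do not support that. No section classes a known death as missing, death is not a PP exclusion, and the plan's own description of the mRS includes death. On that reading a death is an observed value outside 0-2 and stays in, and the whole 2 to 9 point effect disappears. The same limit applies to the inference that the rate would hold steady or rise as deaths accumulate over 5 years: it follows only if deaths are dropped. What remains is a missing rule with a plausible bad outcome.

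It can also be said that section 10 describes itself as general and defers data derivations to a separate SAP. That could settle how death is scored. It is less likely to settle the analysis set, because section 10 says the SAP will reflect the protocol, and section 10.3.5 already fixes PP and observed data.

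Three further points stand. The endpoint has no hypothesis or performance goal and does not enter study success. Deaths, serious events and neurologic events are summarised on the mITT set (section 10.3.7), so deaths would be visible elsewhere in the report. PP is the plan's consistent choice for effectiveness, including the primary effectiveness endpoint. That choice is less apt for a functional outcome that an unsuccessful attempt can worsen.

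**Conclusion.** The exclusion of failed implants and of major eligibility or DAPT deviators from the mRS 0-2 rate follows directly from sections 10.3.5 and 10.1.6. The handling of death is unstated, and the observed-data rules make dropping deaths a plausible result. The good-outcome rate may therefore be overstated; the documents do not show that it will be.

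The size rests on assumptions. If deaths are dropped, with 88% of survivors at mRS 0-2 and 2% to 10% deaths, the excess is about 2 to 9 points. The failed-implant part is small in the illustration and can go either way; with no failed implants it is zero. The point should be corrected because this is a pre-specified secondary endpoint, and the only listed functional-status endpoint at 3 and 5 years, in a study meant to support a premarket approval application. It does not threaten the study's success criteria.

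**What to change.** In section 10.3.5, and in the SAP derivations:

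1. Analyse mRS 0-2 at 1 year on the mITT set.
2. State that death before a visit, from any cause, counts as not mRS 0-2 at that and all later time points.
3. Give the PP observed-data rate as supporting.
4. At 3 and 5 years, count deaths in the same way and state the denominator and who is in it. Failed-implant subjects are followed only up to 1 year, so a full mITT rate is not available at those times.

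The cost is a change of wording. The 1-year analysis needs no new data collection, since failed-implant subjects are already followed to 1 year and only their DSA is waived. The descriptive rate is likely to be slightly less favourable. Study success, power and sample size are unaffected.
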